### 9.1.2 Supplementary Analysis

The following supplementary analyses will be undertaken using the mITT population, unless otherwise noted:

- Repeat of the primary endpoint analysis, based on the PPS.
- Repeat of the primary endpoint analysis, excluding all patients who received additional therapies that could impact the primary endpoint at any time until the

---

day GI2 is achieved or Day 10 or withdrawal or discharge day, whichever comes first. The list of all patients who received additional therapies that could impact the primary endpoint at any time until achievement of the GI2 endpoint or completion of the study will be provided by the Shionogi Medical Monitor prior to database lock and unblinding.

- For each treatment group, a two-way table summarizing the proportion of patients by achievement of GI2 until 240 hours (yes/no) and additional therapies received that could impact the primary endpoint at any time (yes/no) until Day 10 or withdrawal or discharge day, whichever comes first.
- Proportion of patients achieving GI2 by treatment group and cumulative day. As for the definition of cumulative day, if patients achieved GI2 on a certain day, GI2 will be considered as sustained through Day 10 or withdrawal or discharge day, whichever comes first (called “last day”). Pairwise comparison as Cochran Mantel Haenszel test adjusted by surgical procedure will be applied to the proportion at Day 10.
- Proportion of patients achieving GI2 by treatment group, surgical procedure, and cumulative day.

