9.4.5.1 Primary Efficacy Endpoint

The primary endpoint will be time from the end of surgery (defined as the time the patient leaves the operating room) to time to first toleration of solid food (defined as the time when the patient consumes a meal that requires chewing and has no significant nausea or vomiting, as per the judgment of the investigator, for 4 hours after that solid food) and first bowel movement (GI2).

The mean survival time, which is also referred to as the RMST, of GI2 events within 240 hours will be estimated using the area under the Kaplan-Meier (KM) curve. To demonstrate the linear dose-response relationship between treatment groups (3 naldemedine groups and placebo group) and the RMST, the linear contrast test for trend with contrast coefficients of (-3, -1, 1, 3) will be performed. If a dose-response relationship is detected, then pairwise comparisons of the RMST between each dose group of naldemedine and the placebo group will be conducted, and the treatment differences (with its 95% confidence interval [CI]) will be provided. If an event does not occur during the evaluation period of 240 hours, the patient will be censored at the time of his/her last nonmissing postbaseline assessment. The same analysis will be performed in the Per Protocol set. In addition, the reason for discharge prior to having the first bowel movement will be listed.

Patients will continue to be evaluated for efficacy regardless of treatment adherence. The use of additional therapies or interventions that could treat any component of the primary endpoint (eg, motility agents, anti-emetics, laxatives, etc), may confound the results of the primary efficacy analysis. This list of therapies will be finalized before database lock. To examine this issue, the following exploratory analyses of the GI2 endpoint will be performed or provided:

- Repeat of the primary analysis, excluding all patients who received additional therapies at any time postrandomization that could treat any of the components of the GI2 endpoint. It is recognized that this subset is selected based on postrandomization decisions, may be confounded with the treatment group, and may not represent a randomized subgroup of the primary endpoint.
- Table of proportion of patients in each treatment group who received additional therapies that could treat any of the GI2 components.

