- Two-way table summarizing each patient's status at the end of the trial regarding receipt of an additional therapy that could treat any of the GI2 components and whether the GI2 endpoint was achieved. For example, the rows can be yes/no for GI2 endpoint achieved, and the columns can be receipt of additional therapy. This

table will be done during the evaluation period of 240 hours for patients and by treatment group.

- Proportion of patients in each group that achieve the GI2 endpoint, regardless of use of additional therapies that could treat any of the GI2 components. This will be tabulated cumulatively by day. The cumulative proportions achieving the GI2 endpoint will be compared at Day 10 with the difference in proportions and an associated 95% CI will be provided.
- Proportion of patients in each group that achieve the GI2 endpoint, where the use of additional therapies that could treat any of the GI2 components included in the analysis as a patient failure to achieve the GI2 endpoint, beginning with the day the patient first receives the additional therapy. This will be tabulated cumulatively by day. The cumulative proportions achieving the GI2 endpoint will be compared at Day 10, with the difference in proportions and an associated 95% CI provided.

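### SAP 9.1.2 drops, without the required justification, the protocol's GI2 analysis that counts additional therapy as failure and the Day 10 difference with 95% CI, and its remaining therapy checks use windows that end at discharge or conflict

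*SAP*

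**What the plan says.** Protocol 9.4.5.1 (Primary Efficacy Endpoint) warns that motility agents, anti-emetics, laxatives and similar treatments may confound the primary result. It lists five exploratory checks on GI2:

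1. The primary analysis run again, "excluding all patients who received additional therapies at any time postrandomization that could treat any of the components of the GI2 endpoint". The protocol adds that this subset "may be confounded with the treatment group, and may not represent a randomized subgroup of the primary endpoint".
2. A table of the proportion in each group receiving such therapies.
3. A two-way table of therapy against GI2, over the 240-hour evaluation period.
4. The cumulative GI2 proportion by day whatever therapy was used, which is to be "compared at Day 10 with the difference in proportions and an associated 95% CI will be provided".
5. The same cumulative proportion with additional therapy "included in the analysis as a patient failure to achieve the GI2 endpoint, beginning with the day the patient first receives the additional therapy", again with a Day 10 difference and 95% CI.

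Protocol 9.4 says that changes from its analyses are to be set out and justified in the SAP.

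SAP 9.1.2 (Supplementary Analysis) lists a per-protocol repeat, a repeat excluding therapy users, a two-way table, cumulative GI2 by day, and the same by surgical procedure. For cumulative GI2, "if patients achieved GI2 on a certain day, GI2 will be considered as sustained through Day 10 or withdrawal or discharge day, whichever comes first"; then "Pairwise comparison as Cochran Mantel Haenszel test adjusted by surgical procedure will be applied to the proportion at Day 10". The two-way table crosses GI2 up to 240 hours with "additional therapies received that could impact the primary endpoint at any time (yes/no) until Day 10 or withdrawal or discharge day, whichever comes first". The exclusion analysis removes patients treated up to the earliest of GI2, Day 10, withdrawal and discharge, but the patient list it draws on covers therapy "at any time until achievement of the GI2 endpoint or completion of the study".

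**The concern.** The primary analysis counts GI2 regardless of rescue. If rescue use differs between groups, the RMST differences partly reflect the rescue. The protocol anticipated this, and its fifth check is the only one that works by day, keeps the whole mITT Population and gives no credit for recovery after additional therapy. Its loss leaves a subset chosen after randomization, which the protocol itself distrusts, and a table that does not show whether therapy came before or after GI2.

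The two-way table also has mismatched clocks. GI2 can be reached after discharge, because protocol 8.1.1.1 and note t of the Schedule of Activities follow the first bowel movement daily to Day 10. Therapy stops being counted at discharge. At stake is how well the trial can support its reading of the primary result when a dose is chosen, not the primary test itself.

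**Working it through.** **Step 1. Protocol checks against the SAP.**

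| Protocol 9.4.5.1 | SAP 9.1.2 |
|---|---|
| Exclusion of therapy users at any time after randomization | Kept, with a shorter window; no reason given |
| Proportion receiving therapy | Not listed separately; available as the margin of the two-way table, within that table's window |
| Two-way table over 240 hours | Kept; GI2 to 240 hours, therapy to the earliest of Day 10, withdrawal and discharge |
| Cumulative GI2 regardless of therapy, Day 10 difference and 95% CI | Proportions kept; difference and CI replaced by a stratified CMH test |
| Cumulative GI2 with therapy as failure, Day 10 difference and 95% CI | Absent |

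**Step 2. Is it elsewhere in the SAP?** No.
- SAP 9.3.8 gives by-day GI2 with a CMH test and no therapy rule.
- SAP 9.3.9 compares laxative use, but only during study drug exposure. Under protocol 4.1, dosing ends at GI2 or the discharge order, whichever is first, so use at home is not counted.
- SAP 9.1.3 has no therapy subgroup.
- There is no section on changes from the protocol. SAP 1 covers only later deviations from the final SAP.

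**Step 3. Trace one hypothetical patient.** The patient tolerates solid food, is discharged on day D without a bowel movement, takes a laxative on D+1 and has a first bowel movement on D+2, within 240 hours.
- Two-way table: GI2 yes, therapy no.
- Exclusion analysis: kept under its stated window, removed under its list.
- SAP 9.3.9: not counted.
- Protocol's fifth check: failure from D+1.
- SAP cumulative analysis: achieved on D+2. The rule as written carries GI2 only to a discharge that has already passed.

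**Step 4. What can be calculated.** The documents give no Day 10 GI2 proportion, therapy-use rate or discharge distribution, so the plan has no figure to reproduce. Two illustrations follow.

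*Width of the omitted interval.* Unstratified Wald half-width = 1.96 × √(2p(1−p)/n), with the same assumed p in both groups. Protocol 9.2 gives 44 and 85 per group; the synopsis gives about 50.

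| Assumed p | n = 44 | n = 50 | n = 85 |
|---|---|---|---|
| 0.80 | 16.7 points | 15.7 | 12.0 |
| 0.90 | 12.5 points | 11.8 | 9.0 |

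For example, at p = 0.80 and n = 50: 1.96 × √(2 × 0.16/50) = 1.96 × 0.08 = 0.157. This is the trial's precision at Day 10, not the effect of the omission.

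*How far checks 4 and 5 can differ.* Assume Day 10 GI2 of 86% on placebo and 94% on active treatment, a difference of 8 points, with n = 50 per group. Let r be the share of achievers who had therapy before GI2. With therapy as failure, each proportion becomes p(1−r).
- r = 30% in both groups: 0.86 × 0.70 = 60.2% and 0.94 × 0.70 = 65.8%. Difference 5.6 points (95% CI −13.3 to 24.5).
- r = 30% on placebo and 15% on active: 60.2% and 0.94 × 0.85 = 79.9%. Difference 19.7 points (95% CI 2.2 to 37.2).

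All these rates are assumed. They show that the omitted check can tell a different story from the retained one, not that it will.

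**The case against.** The best case for the SAP is that these analyses are exploratory, the document is version 1, and much remains. Group proportions by cumulative day are tabulated, SAP 9.1.1 gives pairwise RMST differences with 95% CIs, and laxative use is compared in 9.3.9. All of that is true and limits the weight of the point. It does not supply the fifth check, and protocol 9.4 makes no exception for exploratory analyses when it asks for justification. Table shells may add detail, but the protocol names the SAP as the place for the reason.

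A reader might infer more than the documents support:
- *That only a p-value is left.* No. The Day 10 difference follows by subtraction from the tabulated proportions. What is lost is its planned reporting with a CI.
- *That patients with GI2 lose that status at discharge.* The analysis is cumulative and in the mITT Population, and a recorded GI2 time is observed data, so the observed-cases rule in SAP 6.4 does not remove it. Carry-forward is the natural reading. The wording only needs tidying, chiefly for GI2 first reached after discharge.
- *That the exclusion analysis certainly misses therapy at home.* If its list governs, it does not. The defect there is inconsistency. The firm statement applies to the two-way table.
- *That SAP 9.3.8 also departs from the protocol by having no CI.* Protocol 9.4.5.3 promised only a summary by treatment group for that endpoint.
- *That the 20% in protocol 9.2 is the share without GI2.* It is an assumed rate of independent censoring within 240 hours, and so does not count the patients affected here.

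**Conclusion.** The point holds as an unexplained departure from the protocol's own exploratory plan. One analysis is missing, one estimate with its interval has been replaced by a test, the two-way table scores therapy taken between discharge and GI2 as no therapy, and the exclusion analysis has two windows. The first two rest on the text alone. The third matters only to the extent that patients go home before GI2 and are then treated, and the documents give no rate for that. The size of the effect on any reported result therefore cannot be derived. The primary RMST trend test and its pairwise comparisons are untouched. This should be corrected, but it does not threaten the trial's main inference.

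**What to change.** Amend SAP 9.1.2 before unblinding:

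- (a) Reinstate the therapy-as-failure cumulative analysis in the mITT Population, with the Day 10 difference from placebo and its 95% CI. State how therapy first given on the day of GI2, or after it, is scored. Protocol 6.5 lists only start and end dates for medication, so order within a day may not be recoverable. If the sponsor still prefers to omit the analysis, protocol 9.4 requires the reason in the SAP.
- (b) Add the Day 10 difference from placebo with 95% CI to the retained cumulative analysis, alongside the CMH test.
- (c) Use one therapy window in the exclusion analysis, its patient list and the two-way table: to GI2 or, for patients without GI2, to Day 10 or withdrawal. It should not end at discharge.
- (d) As a minor clarification, state that GI2 once achieved, including after discharge up to Day 10, is carried forward to Day 10.

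The cost is SAP text, one reinstated table and an interval added to another. The data are already planned: bowel movements are followed to Day 10, and medication received during the study is recorded with dates. One limit remains. The daily contact after discharge is specified for the first bowel movement only, so capture of therapy at home depends on the concomitant medication record.

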### **9.1.3 Subgroup Analysis**

RMST will be calculated and two types of KM curve with 95% confidence bound and point estimate line only will be provided by following subgroups.

- Surgical procedure (Small bowel resection with primary anastomosis, large bowel resection with primary anastomosis, or radical cystectomy requiring bowel transection with primary anastomosis)
- Prior surgery (No prior surgery, 1 prior surgery, 2 prior surgeries)
- Epidural anesthesia (yes/no)
- Enhanced recovery protocol (all aspects of ERP versus those that had only the 3 that were mandated)

## **9.2 Secondary Endpoints**

### **9.2.1 Time from the End of Surgery to Time when the Discharge Order is Written**

The time from the end of surgery to time when the discharge order is written will be the hours between date and time of surgery and date and time of writing the discharge order. The censoring will be defined in the same manner as defined for the primary endpoint.

#### **9.2.1.1 Analysis**

Pairwise comparison will be applied to the time from the end of surgery to time when the discharge order is written in the same way as described in section 9.1.1. A Kaplan-Meier curve will be provided by treatment group.

## **9.2.2 Proportion of Patients Requiring Postoperative Re-insertion of the Nasogastric Tube**

The proportion of patients requiring postoperative re-insertion of the nasogastric tube will be calculated based on the number of patients requiring postoperative re-insertion of the nasogastric tube. Patients in the mITT Population who do not have postoperative re-insertion of the nasogastric tube will be excluded from the denominator.

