8.1.2.2 Reinsertion of the Nasogastric Tube

Whether a patient requires reinsertion of the nasogastric tube at any time during the postoperative treatment period will be recorded in the eCRF as yes or no along with the duration of the reinsertion (if applicable).

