9.4.5 Efficacy Analyses

The mITT Population will be the primary population for efficacy analyses.

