9.4.5.2 Secondary Efficacy Endpoints

Secondary efficacy endpoints will be as follows:

- Time from the end of surgery (as defined for the primary endpoint) to time when the discharge order is written
- Proportion of patients requiring postoperative reinsertion of the nasogastric tube
- Proportion of patients with nausea on Days 1 through 3
- Proportion of patients with vomiting on Days 1 through 3
- Proportion of patients discharged by Day 10 who are readmitted for any reason within 30 days after discharge from the hospital

For time from the end of surgery to time when the discharge order is written, the same KM approach as used for the primary efficacy analysis will be performed. The proportion of patients for each of the other parameters will be summarized by treatment group.

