### **9.2.2.1 Analysis**

Pairwise comparison as Cochran Mantel Haenszel test adjusted by surgical procedure will be applied to the proportion.

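### SAP 9.2.2 drops every patient without nasogastric tube re-insertion from the denominator, so the proportion is 100% in any arm with an event, undefined in an arm without one, and cannot be compared

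*SAP*

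**What the plan says.** The protocol lists the endpoint among the secondary efficacy endpoints (Section 9.4.5.2) as "Proportion of patients requiring postoperative reinsertion of the nasogastric tube", with no restriction on who is counted. Section 8.1.2.2 says that re-insertion during the postoperative treatment period "will be recorded in the eCRF as yes or no along with the duration of the reinsertion". Section 9.4.5 sets the analysis population: "The mITT Population will be the primary population for efficacy analyses". For this and the other proportion endpoints, Section 9.4.5.2 asks for a summary: "The proportion of patients for each of the other parameters will be summarized by treatment group".

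SAP 9.2.2 says that the proportion is "calculated based on the number of patients requiring postoperative re-insertion of the nasogastric tube", and then adds the denominator rule: "Patients in the mITT Population who do not have postoperative re-insertion of the nasogastric tube will be excluded from the denominator". SAP 9.2.2.1 gives the test: "Pairwise comparison as Cochran Mantel Haenszel test adjusted by surgical procedure will be applied to the proportion".

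**The concern.** A proportion needs both events and non-events in its denominator. The SAP rule removes the non-events, so what is left is the set of patients already in the numerator. The result carries no information about how often re-insertion happened in any arm.

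At stake is one of five named secondary efficacy endpoints. If the SAP is followed, the endpoint can show no difference between any naldemedine dose and placebo, in either direction. If the error is noticed only after unblinding, the replacement denominator will be chosen with treatment results in view.

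**Working it through.** The documents give no expected re-insertion rate, power or sample size for this endpoint, so there is no planned figure to reproduce. The check applies the SAP rule literally.

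**The proportion.** Let n be the mITT patients in an arm and r those with re-insertion.

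- Numerator (SAP 9.2.2): r.
- Patients removed from the denominator: n − r.
- Denominator: n − (n − r) = r.
- Proportion: r/r = 1.00 for every r > 0, and 0/0 for r = 0, whatever n is.

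**The test.** In each surgical stratum, let a and b be re-insertion yes and no on placebo, c and d the same on active drug, and N = a + b + c + d. The CMH statistic is

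[Σ(a − (a+b)(a+c)/N)]² / Σ[(a+b)(c+d)(a+c)(b+d) / (N²(N−1))].

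Under the SAP rule b = d = 0 in every stratum. Then N = a + c, and each numerator term is a − a(a+c)/(a+c) = 0. Each variance term contains the factor (b+d) = 0. The statistic is 0/0.

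**Illustration, placebo against 5 mg, 50 per arm.** All counts and stratum sizes here are assumed. The strata have 10, 30 and 10 patients per arm, with re-insertions of 1, 5, 2 on placebo and 0, 2, 1 on 5 mg.

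- SAP rule: 8/8 = 100% and 3/3 = 100%; CMH numerator 0, variance 0, no p-value.
- All mITT patients in the denominator: 8/50 = 16.0% and 3/50 = 6.0%. The numerator terms are 0.5 + 1.5 + 0.5 = 2.5 and the variance terms are 0.250 + 1.572 + 0.671 = 2.493. Chi-square = 2.5²/2.493 = 2.51.

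**The planned size range.** SAP 4.2 gives 44 to 85 mITT patients per group. The same calculation, again with assumed counts:

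| n per arm | Placebo, 5 mg events | SAP rule | mITT denominator | CMH chi-square (mITT) |
|---|---|---|---|---|
| 44 | 6, 3 | 100%, 100%; test undefined | 13.6%, 6.8% | 1.08 |
| 50 | 8, 3 | 100%, 100%; test undefined | 16.0%, 6.0% | 2.51 |
| 85 | 13, 6 | 100%, 100%; test undefined | 15.3%, 7.1% | 2.86 |

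**Search for a repair elsewhere.** SAP 9 sets mITT as the efficacy population unless otherwise specified, and 9.2.2 specifies otherwise. SAP 6.4 (no imputation, observed cases) deals with missing values, not with recorded negatives. SAP 9.2.5.1, 9.3.3.1, 9.3.8.1 and 9.3.9.1 refer back to 9.2.2.1 for the test only, so the faulty denominator does not spread to them.

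**The case against.** The best reply is that this is a drafting slip with a recoverable meaning. The protocol defines the endpoint over patients, collects a yes or no and names mITT for efficacy. The authors may have meant to exclude patients with no re-insertion data, which would fit SAP 6.4. The data are collected whatever the SAP says, and a table showing 100% in both arms would be caught at the first dry run. The table shells are a separate document and may already be right. The endpoint is secondary in a Phase 2 trial without multiplicity adjustment, the protocol asks only for a summary by group, and the CMH test comes from the SAP. Power would be modest even after correction: with assumed true rates of 10% and 5% it is 0.14 at 44 per arm and 0.23 at 85; with 20% and 5% it is 0.57 and 0.85.

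Much of this stands. No data are lost, and the consequence is limited to this endpoint. But the stated rule still cannot be computed, and its intended replacement is not unique. It could be all mITT patients, mITT patients with a recorded answer, or only patients who had a tube in the first place. These can give different denominators. Protocol 9.4 requires changes from its analyses to be justified in the SAP, and none is given here. SAP 1 requires deviations from the final SAP to be documented in the study report, so even a sensible silent correction would be a reportable deviation.

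**Conclusion.** The concern holds. As written, the endpoint equals 100% in every arm with at least one re-insertion and is undefined in an arm with none, and the planned test does not exist. This rests on the wording and on arithmetic; the event counts above only illustrate it and say nothing about likely effect size. The loss is complete for the analysis as specified, but the underlying yes/no data remain available and the endpoint can be fully restored. The primary endpoint and the sample size are untouched. It must be corrected before unblinding because the specified analysis cannot be carried out.

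**What to change.** Replace the denominator sentence in SAP 9.2.2 with text such as:

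> *The denominator is all mITT patients with a recorded yes or no for re-insertion of the nasogastric tube after surgery. A recorded no is a non-event. Patients whose status is not recorded are left out, and their number is reported by treatment group.*

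This agrees with the no-imputation rule in SAP 6.4 and Protocol 9.4. Counting an unrecorded status as a no would conflict with that rule and could understate the rate among patients who withdraw early.

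The sponsor should also state whether patients who never had a tube are included, and check that the table shells use the same denominator. The cost is a few sentences in the SAP, made before unblinding, with no new data and no change to the protocol.
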